## 3.1 STUDY PARAMETERS

## 3.1.1 Safety Parameters

The safety of acalabrutinib and pembrolizumab will be characterized by the type, frequency, severity, timing of onset, duration, and relationship to study drug(s) of any treatment-emergent AEs or abnormalities of laboratory tests; SAEs; ECIs, or AEs leading to discontinuation of study treatment.

For consistency of interpretation, AEs will be coded using the Medical Dictionary for Regulatory Activities (MedDRA), and the severity of AEs and laboratory abnormalities will be graded using the Common Terminology Criteria for Adverse Events (CTCAE), Version 4.03 or higher. Standard definitions for seriousness will be applied (see Section 6.1).

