# 6.2.1 Adverse Event Reporting Period

After the signing of the ICF and prior to the first dose of study drug, all SAEs must be reported. After the first dose of study drug, all AEs/SAEs, irrespective of attribution of causality, must be reported.

For acalabrutinib, all AEs will be reported until 30 days after the last dose of acalabrutinib or the start of new anticancer therapy (whichever comes first). After this period, investigators should report SAEs or other AEs of concern that are believed to be related to prior treatment with acalabrutinib.

For pembrolizumab, all AEs must be reported through 30 days after the last dose of pembrolizumab; any SAEs, or follow-up to an SAE, including death due to any cause other than progression of the cancer under study, must be reported through 90 days after the last dose or 30 days after the last dose of pembrolizumab if the subject initiates a new anticancer therapy within the 90-day posttreatment timeframe.

SAEs considered related to study drug(s) or study procedures occurring after the end of the AE reporting period (as defined above) must be reported.

All AEs and SAEs that occur during the reporting period should be followed to resolution or until the investigator assesses the subject as stable, the subject is lost to follow-up or withdraws consent. Resolution/stable means the subject has returned to baseline state of health or the investigator does not expect any further improvement or worsening of the event.

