# 6.2.2 Assessment of Adverse Events

Investigators will assess the occurrence of AEs and SAEs at all subject evaluation timepoints during the study. All AEs and SAEs whether volunteered by the subject, discovered by study personnel during questioning, or detected through physical examination, or other means, that occur to any subject from the time of first dose through 30 days following the cessation of study drug(s), and all SAEs that occur to any subject receiving pembrolizumab from the time of first dose through 90 days following cessation of pembrolizumab, or 30 days following cessation of pembrolizumab if the subject initiates new anticancer therapy (whichever is earlier) will be recorded in the subject's medical record and on the AE CRF.

Disease progression itself is not considered an AE unless it is considered to be drug-related by the investigator; however, signs and symptoms of disease progression may be recorded as AEs or SAEs.

Each recorded AE or SAE will be described by its diagnostic term, duration (e.g., start and end dates), severity, regulatory seriousness criteria, if applicable, suspected relationship to the study drugs (see following guidance), and any actions taken. The causality of AEs to the study drugs will be assessed by means of the question: 'Is there a reasonable possibility that the event may have been caused by the study drugs?' per FDA guidance on safety reporting requirements (FDA Drug Safety Communication 2012).

See Appendix 3 for more detail on assessing causality.

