- Subjects who are anti-HBc positive (or have a known history of HBV) should have a quantitative PCR test for HBV DNA performed during screening and while on study treatment. These subjects should have a quantitative PCR test performed monthly while on combination treatment and every 3 months while on acalabrutinib monotherapy. Following study drug discontinuation, monitoring should continue every 3 months until 12 months after last dose of study drug(s). Any subject with a rising viral load (above lower limit of detection) should discontinue study drug(s) and have antiviral therapy instituted and a consultation with a physician with expertise in managing hepatitis B. As IVIG may cause false positive serology, monthly PCR testing is not required in subjects who are currently receiving or received prophylactic IVIG within 3 months before study enrollment and have a documented negative anti-HBc test before the initiation of IVIG therapy. Additional PCR testing should be performed when clinically indicated (e.g., in the setting of rising transaminase levels).
- x Subjects with a known history of hepatitis C or who are hepatitis C antibody-positive should have quantitative PCR testing for HCV DNA performed during screening and at Weeks 13 and 25. No further testing beyond Week 25 is necessary if PCR results are negative.
- y For subjects who have an allogeneic SCT within 24 months of last dose of pembrolizumab, transplant parameters will be collected, and specific events will be collected for 18 months from the date of the allogeneic transplant, to include graft-versus-host-disease (acute and/or chronic), veno-occlusive disease, febrile syndrome (a steroid-requiring febrile illness without an infectious cause), and encephalitis, for all grades, and regardless of relationship to study drug. Additional medically important adverse events post-allogeneic SCT may be submitted at the investigator's discretion. If available and relevant to an event post-allogeneic SCT, concomitant medications and/or laboratory results may also be reported.
- z After the end of the protocol-defined AE reporting period, only SAEs considered related to study drug(s) or study procedures are required to be collected.

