9.7.1 Adverse Events

The Medical Dictionary for Regulatory Activities (MedDRA) will be used to code all AEs to a system organ class and a preferred term. The severity of the AE will be assessed by National Cancer Institute (NCI) Common Terminology Criteria for Adverse Events (CTCAE) Version 4.03 or higher. Drug-related AEs are those assessed by investigator as related.

Treatment-emergent AEs are defined as those events that occur (actual or imputed start date) on or after the first dose of study drug, through the treatment phase, and within 30 days following the last dose of study drug.

Treatment-emergent AEs will be summarized by system organ class and preferred terms in descending order of frequency, by NCI toxicity grade and by relationship to study drug. The same summary will be provided for serious treatment-emergent AEs and drug-related serious treatment-emergent AEs, treatment-emergent AEs leading to treatment discontinuation, dose reductions and dose withheld.

Death information is reported in the study exit CRF for all deaths. Incidences of deaths are to be reported, along with the primary cause of death.

AE by subject listing and death listing will be provided.

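### SAP 9.7.1 summarises SAEs only to 30 days after the last study drug, so later non-fatal SAEs that the protocol collects are in no summary table

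*SAP*

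**What the plan says.** **SAP.** Section 9.7.1 defines treatment-emergent events as those starting on or after the first dose, "through the treatment phase, and within 30 days following the last dose of study drug". The SAE summaries it plans are for "serious treatment-emergent AEs and drug-related serious treatment-emergent AEs". Two other outputs could hold a later event. One is the death summary, which has no 30-day limit: "Incidences of deaths are to be reported, along with the primary cause of death". The other is the by-subject AE listing, for which no window is stated. SAP 4.1 names treatment-emergent AEs and SAEs as the safety endpoint.

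**Protocol, collection.** Section 6.2.1 says that SAEs "must be reported through 90 days after the last dose" of pembrolizumab, shortened to 30 days if new anticancer therapy starts within the 90 days. Section 6.2.2 repeats the longer window for all SAEs, "from the time of first dose through 90 days following cessation of pembrolizumab". Section 6.2.1 also requires reporting of "SAEs considered related to study drug(s) or study procedures occurring after the end of the AE reporting period". Appendix 5, footnote z, agrees that after that period "only SAEs considered related to study drug(s) or study procedures are required to be collected". Neither place sets an end date for these related events.

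**Protocol, analysis.** Section 5.5.1 plans frequencies of treatment-emergent AEs and has no separate summary of later SAEs. Section 3.1.1 lists the safety parameters as any "treatment-emergent AEs or abnormalities of laboratory tests; SAEs; ECIs, or AEs leading to discontinuation of study treatment".

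**The concern.** The trial's primary objective is to characterise safety (protocol 2.1, SAP 2.1). Protocol 3.8.2 warns that immune-related events can begin several months after pembrolizumab stops. Section 3.10.2.2 adds that such reactions usually occur during treatment but can follow it. The protocol therefore collects SAEs for longer than other adverse events, yet the SAP has no table that uses the additional period.

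A listing shows individual events but gives no frequency by preferred term, grade or relationship. Leaving the later events out of the tables can only lower the reported SAE and related-SAE counts. The remaining question is how long the untabulated period is, and for whom.

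**Working it through.** The plan gives no figure to reproduce; the check compares two windows.

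**Inputs**
- P = day of last pembrolizumab, A = day of last acalabrutinib, and d = A − P, set to 0 if pembrolizumab is the last drug given.
- End of the SAE tables: max(P, A) + 30 (SAP 9.7.1). This reads the last dose of study drug as the later of the two drugs. The SAP does not say so for a two-drug regimen, but this reading gives the smallest gap.
- End of all-cause SAE collection with no new anticancer therapy: max(P + 90, A + 30) (protocol 6.2.1, the pembrolizumab and acalabrutinib rules together).

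**Gap with no new anticancer therapy within 90 days**

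Gap = max(P + 90, A + 30) − [max(P, A) + 30]. Putting A = P + d gives max(P + 90, P + d + 30) − (P + d + 30) = max(0, 60 − d).

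| d (days) | Tables end | Untabulated days | Share of the 90 days |
|---|---|---|---|
| 0 | P + 30 | 60 | 60/90 = 67% |
| 14 | P + 44 | 46 | 46/90 = 51% |
| 21 | P + 51 | 39 | 39/90 = 43% |
| 30 | P + 60 | 30 | 30/90 = 33% |
| 45 | P + 75 | 15 | 15/90 = 17% |
| 59 | P + 89 | 1 | 1/90 = 1% |
| 60 or more | P + 90 or later | 0 | 0% |

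**Gap with new anticancer therapy at any time within the 90 days.** The pembrolizumab window shortens to P + 30 and the acalabrutinib window ends no later than A + 30. The tables already run to max(P, A) + 30, so the all-cause gap is 0 for every d.

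**Related SAEs.** Collection has no end date. A related SAE starting after max(P, A) + 30 is outside the tables whatever d is.

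**Partial dates.** Under SAP section 8, an imputed start that falls after last dose + 30 days but in the same month is set to last dose + 30 days. Some late SAEs with incomplete dates are therefore tabulated; those with full dates are not.

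**How late events are found.** The safety follow-up visit is 30 days (+7) after the last dose (protocol 4.3). The adverse-events row of Appendix 5 is marked up to that visit and has no mark in the 12-weekly follow-up column. Essentially all of the untabulated period, for all-cause and related SAEs alike, falls after the last scheduled AE assessment.

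**Number of events.** The documents give neither the distribution of d nor the timing of SAEs relative to the last dose, so no count can be computed.

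**The case against.** The strongest reply is that the SAP does what the protocol's analysis section asks. Protocol 5.5.1 and SAP 4.1 both speak of treatment-emergent events. A 30-day window is ordinary, and it matches the general AE period (6.2.1), the period for events of clinical interest (6.2.6) and, broadly, the laboratory window (SAP 9.7.2). It also keeps ascertainment uniform, whereas events after day 30 come from unscheduled reporting over windows of unequal length. Late deaths are summarised, late SAEs may be listed, and no hypothesis test depends on these tables (SAP 5). All of this stands. It is why the main tables should not change, and why added events need a label. It does not give the later non-fatal SAEs a frequency anywhere.

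Two stronger readings are tempting, and the documents do not support them:

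- A reader might infer from protocol 3.1.1 that SAEs are a parameter separate from treatment-emergent AEs, so that the SAP breaks the protocol. The sentence is ambiguous: the words treatment-emergent may govern the whole list, and SAP 4.1 reads it that way.
- A reader might size the gap for a typical subject from the median exposure of 3.4 months in protocol 1.4.2.1. That is 3.4 × 365.25/12 = 103.5 days. With acalabrutinib to day 103 and three-weekly pembrolizumab last given on day 85, d = 18 and the gap is 60 − 18 = 42 days. But that section does not say which drug the figure describes, and it may include subjects still on treatment. The result also assumes no new therapy within 90 days, which is uncertain because confirmed progression ends study treatment (3.6). It describes a constructed subject, not the trial.

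**Conclusion.** The point holds as an omission in the planned summaries. Non-fatal SAEs that the protocol requires, and that start more than 30 days after the last study drug, are in no summary table, apart from some with partial dates. The all-cause gap is at most 60 of the 90 days. It reaches that maximum when acalabrutinib stops with or before pembrolizumab, and it is zero once acalabrutinib continues for 60 days or more, or if new anticancer therapy starts within the 90 days. Late related SAEs are untabulated for any d. These figures assume that the last dose is that of the later drug. The events are not lost, since they can appear in the listing, and the number affected may be small. Adding a summary is a cheap improvement to reporting on the primary objective, not the repair of a conflict between the documents.

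**What to change.** Keep the 30-day treatment-emergent definition, the main AE and SAE tables and the SAP section 8 imputation rule. In SAP 9.7.1:

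1. State that the last dose of study drug means the later of the two drugs.
2. Add one supplementary summary on the All-treated population:
   - (a) every SAE in the serious treatment-emergent table, plus later SAEs within the protocol's collection window (90 days after the last pembrolizumab, or 30 days if new anticancer therapy starts within those 90 days), by preferred term, grade and relationship;
   - (b) counts only of related SAEs that start after the reporting period and on or before the data cutoff. The cutoff is needed because protocol 3.6 keeps SAE reporting open after database closure.
3. Label events in both (a) and (b) that fall after the 30-day safety follow-up visit as not collected at scheduled AE assessments.
4. Require that any event in the serious treatment-emergent table is also counted in the supplementary one, so that the two reconcile.

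The cost is one derived flag and one table. No new data are needed: SAEs in the 30- and 90-day windows go on the AE CRF (6.2.2), and all SAEs are reported through the electronic data capture system (6.2.5). The drawbacks are slightly higher SAE counts in the supplementary table and unequal, partly passive ascertainment after day 30, which the label discloses.

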9.7.2 Laboratory Test Results

Laboratory data of hematology, serum chemistry up to 30 days after last dose or the safety follow-up visit date, whichever is later, will be reported in SI units. Applicable laboratory results will be graded according to CTCAE Version 4.03 or higher. Generic normal ranges will be applied whenever reference ranges are not available.

Shift from baseline to the worst grade during the treatment will be provided as shift tables for selected parameters. Figures of changes in selected parameters will be plotted overtime as appropriate.

Urinalysis data will be summarized as appropriate.

By subject lab listing will be provided per each disease group.

9.7.3 Vital Signs

Summary statistics (mean, standard deviation, median, and range) will be produced for vital signs at baseline, maximum, change from baseline to maximum, last value, and change from baseline to last value.

In order to be included in the table, a subject must have both a baseline value and a value for the given post-baseline time point.

By subject lab listing will be provided per each disease group.

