# 1.4.2.1 Safety of Acalabrutinib in Combination with Pembrolizumab for Subjects with B-Cell Malignancies (ACE-LY-005)

Study ACE-LY-005 is a Phase 1b/2, multicenter, open-label proof-of-concept study in subjects with B-cell malignancies. Safety data from 161 subjects are available as of the data cutoff date of 03 September 2017. Median exposure was 3.4 months (range 0.2 to 30.2 months).

All 161 subjects (100.0%) experienced at least 1 AE of any grade. The most frequently reported AEs were diarrhea (44.1%), headache (35.4%), fatigue (33.5%), cough (26.7%), nausea (26.7%), decreased appetite (24.8%), and vomiting (22.4%).

Nine subjects (5.6%) had Grade 5 (fatal) events, including 2 subjects with Grade 5 sepsis and 3 subjects with Grade 5 respiratory failure. One subject with DLBCL had Grade 5 neutropenic sepsis, which was considered by the investigator to be related to acalabrutinib. Two other subjects had Grade 5 events of respiratory failure and sepsis which were considered by the investigator to be related to pembrolizumab.

SAEs were reported for 73 subjects (45.3%). The most commonly reported SAEs were sepsis (5 subjects [3.1%]) and lung infection and AST increased (4 subjects [2.5%] each). Five subjects had SAEs reported by the investigator as related to only acalabrutinib of lymphoma, tumor flare, neutropenic sepsis (fatal event described above), nausea, and syncope.

Fifteen subjects had SAEs that were attributed to both acalabrutinib and pembrolizumab treatment. Of these 15 subjects, 1 subject experienced multiple related events of mental status change, pyrexia, lactic acidosis, and AST increased (Grade 3). Other SAEs related to both acalabrutinib and pembrolizumab were hypotension, dehydration, septic shock, systemic inflammatory response syndrome, ALT increased, Herpes zoster, lymphadenitis, cytokine release syndrome, lymphocyte count decreased, platelet count decreased, pancreatitis, pneumonitis, lymphoma, gastrointestinal hemorrhage, retroperitoneal mass, anemia, hyponatremia, upper gastrointestinal hemorrhage, enteritis, and neck pain.

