Sixteen subjects had SAEs reported by the investigator to be related to only pembrolizumab, including AST increased, anemia, bronchitis, vertigo, orthostatic hypotension, drug-induced liver injury, platelet count decreased, sepsis, lung infection, pneumonitis, respiratory failure, respiratory distress, colitis, hyponatremia, pyrexia, tubulointerstitial nephritis, and systemic inflammatory response syndrome. The AE of drug-induced liver injury was attributed to pembrolizumab due to the known risk for pembrolizumab of immune-mediated hepatitis, and occurred in a subject in whom initial corticosteroid therapy was likely not adequate. The event improved when corticosteroids were again administered per guidance in the pembrolizumab prescribing information (Immune-Mediated Hepatitis, pembrolizumab prescribing information).

A total of 40 subjects (24.8%) had AEs that led to study drug discontinuation, the most frequent of which included ALT increased (8 subjects [5.0%]) and AST increased (7 subjects [4.3%]). One subject discontinued study drug due to an AE of lymphoma, considered by the investigator to be related to acalabrutinib only. Five subjects discontinued study drug due to AEs considered to be related to both acalabrutinib and pembrolizumab, including ALT increased in 2 subjects, and cytokine release syndrome, pneumonitis, and AST increased in 1 subject each. Thirteen subjects discontinued treatment due to AEs considered related

only to pembrolizumab, including 1 or more AEs of ALT increased, AST increased, pneumonitis, deafness neurosensory, neutropenia, bursitis, pneumonitis, colitis, and diarrhea.

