### 4.1.7 Physical Examination, Vital Signs, Height, and Weight

The screening physical examination will include, at a minimum, the general appearance of the subject, height (screening only) and weight, and examination of the skin, eyes, ears, nose, throat, lungs, heart, abdomen, extremities, musculoskeletal system, nervous system, and lymphatic system.

Physical examinations will be done during the treatment period and at the safety follow-up visits. For all subjects except those with MM or MF, the following B symptoms will be collected at each examination:

- Unintentional weight loss of normal body weight over a period of ≤6 months
- Disease-associated intermittent fevers ≥38°C
- Drenching sweats, especially at night

Vital signs (blood pressure, heart rate, and body temperature) will be assessed after the subject has rested in the sitting position.

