# 5.5 ENDPOINT DATA ANALYSIS

### 5.5.1 Safety Endpoint

Safety summaries will include summaries in the form of tables and listings. The frequency (number and percentage) of treatment-emergent AEs will be reported in each treatment group by MedDRA System Organ Class and Preferred Term. Summaries will also be presented by the severity of the AE (per CTCAE, v4.03 or higher) and by relationship to study drug (e.g., either acalabrutinib, pembrolizumab, or both).

Laboratory shift tables containing counts and percentages will be prepared by treatment assignment, laboratory parameter, and time. Summary tables will be prepared for each laboratory parameter. Figures of changes in laboratory parameters over time will be generated.

Results of vital sign assessments, ECGs, and physical examinations will be tabulated and summarized.

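### The vital-sign summary in SAP 9.7.3 has a maximum but no minimum, so falls that recover before the last value are not summarised

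*SAP*

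**What the plan says.** SAP 9.7.3 fixes both the statistics and the points at which they are taken. "Summary statistics (mean, standard deviation, median, and range) will be produced for vital signs", and the points are "vital signs at baseline, maximum, change from baseline to maximum, last value, and change from baseline to last value". Subjects need a baseline value and a value at the post-baseline point concerned. The section ends with a listing: "By subject lab listing will be provided per each disease group".

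Protocol 4.1.7 defines what is measured: "Vital signs (blood pressure, heart rate, and body temperature) will be assessed after the subject has rested in the sitting position". Protocol 5.5.1 adds no detail on how it is summarised: "Results of vital sign assessments, ECGs, and physical examinations will be tabulated and summarized".

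Protocol 1.4.2.1 gives safety data from 161 subjects in this study. For events attributed to both drugs it states: "Other SAEs related to both acalabrutinib and pembrolizumab were hypotension, dehydration, septic shock", and the list continues. Among serious events attributed to pembrolizumab alone it includes "AST increased, anemia, bronchitis, vertigo, orthostatic hypotension, drug-induced liver injury". Protocol 3.10.2.2 lists hypotension among the signs of infusion-related reactions to be monitored.

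**The concern.** For blood pressure and heart rate a low value can be as important as a high one. The table takes an extreme on the high side only. The adverse direction that the protocol itself documents for blood pressure is downward, so the one extreme that is reported points away from it.

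Safety is the primary objective, and SAP 4.1 lists vital signs among the safety endpoints. A reader of the final report would see mean rises to maximum with no matching figure for falls. The neighbouring sections do not have this problem: SAP 9.7.2 uses the worst laboratory grade and SAP 9.7.4 the worst ECOG score. For a fall in pressure, the maximum is not the worst value.

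**Working it through.** The plan gives no figure to reproduce here. The check is a reading of the text, followed by an illustration of size with assumed values.

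**1. Does any other section supply a minimum?**
- Protocol 5.5.1 promises tabulation and summary of vital signs without naming any points. Its shift tables and figures over time are for laboratory parameters.
- SAP 4.1 names vital signs as an endpoint without saying how they are summarised.
- SAP 9.7.3 refers to a given post-baseline time point, but the only such points it lists are the maximum and the last value. No by-visit table and no count below a low threshold is planned.
- SAP 9.7.1 covers adverse events, 9.7.2 laboratory tests, 9.7.4 ECOG status and 9.7.5 physical examinations. None adds a minimum for vital signs.

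**2. One subject (assumed values).** Systolic pressure is 120 at baseline, then 118, 80, 122, 119.
- Maximum 122, change 122 - 120 = +2.
- Last value 119, change 119 - 120 = -1.
- Minimum 80, change 80 - 120 = -40. This is not in the planned table.

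If 80 were instead the last reading, the planned change to last value would be -40 and would appear in that row's range.

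**3. A whole group (assumed model).**
- Number of visits: protocol 1.4.2.1 gives a median exposure of 3.4 months, which is 3.4 × 365.25 / 12 / 7 = 14.8 weeks. Protocol 3.0 sets weekly visits for 8 weeks, then Week 10, then every 3 weeks. With Week 1 as baseline, the post-baseline visits are Weeks 2 to 8 (7 visits), Week 10 and Week 13, so 9.
- Assumptions not in the documents: independent normal within-subject variation, no drug effect, within-subject SD of 5 to 10 mmHg.
- The expected maximum of 9 standard normal values is 1.485. The mean change to maximum by chance alone is 1.485 × SD: 1.485 × 5 = +7.4, 1.485 × 8 = +11.9, 1.485 × 10 = +14.9 mmHg. By symmetry the mean change to minimum is -7.4, -11.9 and -14.9.
- Now let every subject have one 40 mmHg fall at a middle visit, with SD 8. That visit almost never supplies the maximum, so 8 visits remain. The expected maximum of 8 is 1.424, and 1.424 × 8 = 11.4.

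| Mean change from baseline (mmHg, SD 8) | No fall | One transient fall of 40 in every subject |
|---|---|---|
| To maximum (planned) | +11.9 | +11.4 |
| To last value (planned) | about 0 | about 0 |
| To minimum (not planned) | -11.9 | -40.0 |

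The -40.0 comes from simulating this model with one million subjects. The other entries follow from the formulas, and the same simulation agrees with them.

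The planned rows hardly distinguish the two columns; the minimum row does. The no-fall column also shows that either extreme, read alone, suggests a change when there is none.

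**The case against.** The strongest reply is that the table is neither blind to falls nor the main route by which they are reported.

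- **Last-value rows.** Last value and change to last value have no built-in direction and are reported with their range, so a fall still present at the final assessment appears. A fall sustained at every visit would also lower the maximum, if the maximum is taken post-baseline, which the SAP does not specify. This stands. A reader might infer that falls in blood pressure are invisible, or that the table says nothing about them; the documents do not support that.
- **Adverse-event tables.** The events in protocol 1.4.2.1 were reported as serious adverse events. SAP 9.7.1 summarises treatment-emergent and serious events by preferred term, with grade and relationship to drug. This stands as partial cover. Those tables depend on someone judging a reading to be an event, and a summary of measured values is useful because it does not.
- **Reach of the fix.** Readings are taken seated, so a minimum row cannot show a postural drop. A reader might infer that it would detect orthostatic hypotension; it would not. The schedule in protocol Appendix 5 gives vital signs per visit with no post-infusion reading, so some infusion-related falls could be missed too.
- **Chance drift.** Minima drift down as maxima drift up. Adding a minimum balances the table but does not remove that bias.
- **Strength of evidence.** Protocol 1.4.2.1 gives no counts for hypotension, and neither it nor section 3.10.2.2 names bradycardia. The heart-rate part rests on the gap in the table alone.

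Protocol 3.1.1 also leaves vital signs out of the items that characterise safety, but SAP 4.1 names them as an endpoint and protocol 6.0 as a safety assessment.

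**Conclusion.** The point holds in a limited form. As written, SAP 9.7.3 reports an upper extreme and no lower one, no other section fills the gap, and falls that recover before the last value do not enter the vital-sign summary. Hypotension is a reported related serious event in this study and a monitored infusion-reaction sign, so the missing direction is relevant. The last-value rows and the event tables give partial cover.

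The size is small. These are descriptive tables with no hypothesis test (SAP section 5), and no conclusion of the trial turns on them. The mmHg figures rest on the assumed SD, on independence between visits and on 9 visits per subject; they illustrate the mechanism and do not estimate what this trial will show. The change is worth making because it is nearly free and safety is the primary objective.

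**What to change.** In SAP 9.7.3:

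1. Beside the maximum rows, add the post-baseline minimum and the change from baseline to minimum for systolic pressure, diastolic pressure and heart rate. State that the maximum is also taken post-baseline.
2. Add a table note that both extremes drift away from baseline by chance over repeated visits, so neither should be read alone as a drug effect.
3. Correct the listing sentence so that it promises a by-subject vital-signs listing. As it stands it repeats the laboratory section's wording.

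The cost is a few more descriptive rows and one footnote, from data already collected. No visit, procedure or clinical rule changes.
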